Secondary Aims: We will also explore potential within- and between-subject effects of Enhanced HBST versus standard HBST on positive/negative affect, social support, sex risk behavior, and health empowerment.

Overview of the research: During a “start-up” period of 6 months, we will use qualitative methods (focus group [$N=8$], individual interviews [$N=10$]) to inform ongoing consultation with Devicix (an electrical and software engineering firm) on refining a mobile technology for monitoring HBST use, ultimately preparing it for deployment. Then, during the “study phase,” 40 high-risk MSM in the Providence, RI area will be randomly assigned to one of two conditions: An “enhanced” HBST condition ($N=20$) or standard HBST ($N=20$). In both conditions, 3 HBST kits will be sent by mail at 3-month intervals over the course of 6 months (baseline, 3-months, 6-months). We chose to deliver HBSTs by mail given recent evidence that a majority of MSM prefer this method of receiving kits (as opposed to pharmacy pickup or vending machines)^{50,51}. In the “enhanced” HBST condition, mailed test enclosures will be equipped with a mobile monitoring sensor (see Section 3C.3.1.) that triggers an alarm on dedicated mobile phones carried by qualified HIV test counselors (QHTC). QHTCs will then conduct a follow-up call to the user within 24 hours. In the HBST alone condition, test kits will simply be mailed to participants with contact information for local HIV care, confirmatory testing, STI testing, and PrEP. All participants will be oriented to the study during a baseline, in-person appointment at Brown University. Then, participants will complete monthly assessments online over the course of 7 months while on the study (see Fig. 1 for a timeline). To complete the project within the 2-year period, 4 participants per month will be recruited on a rolling basis (beginning in month 6 of year 1), allowing all participants to finish the study by month 10 in Year 2.

C.2 Participant Population

The research has three phases: (1) Focus group phase [$N = 8$], (2) individual interview phase [$N = 10$], and (3) pilot study phase [$N = 40$]. *All* participants (regardless of which phase they are participating in) will meet the same criteria.

Inclusion criteria are as follows:

1. Biologically male
2. Aged 18 or older

3. Have not been tested for HIV in the last year

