Experimental conditions. In this 7-month longitudinal study, 40 participants will be randomized to receive either “enhanced” HBST ($N=20$) or standard HBST ($N=20$). All will have 3 OraSure® test kits shipped to their homes 1-week after baseline, 3-months, and 6-months. Those in the “enhanced” HBST condition will receive follow-up calls within 24 hours after opening their tests. Those in standard HBST will be provided contact information for local services in their test kits, in addition to the information provided by OraSure®.

Measures. Demographics, past HIV testing history, sexual behavior, and other relevant variables will be collected at baseline. Throughout the 7-month study period, participants will complete online assessments each month inquiring about whether they used a study-provided HBST kits in the last month and what the result was. Items will also assess whether they were provided referral to a local agency for additional prevention services (e.g., additional HIV testing, STI testing, PrEP consultation, HIV risk reduction counseling) by a professional in the last month, and whether they sought each service over the last month. Participants will also complete Timeline Follow Back (TLFB^{55,56}) assessments of their sexual behavior over the past month. The TLFB has proven to be one of the more reliable and valid assessments available for sexual behaviors⁵⁷⁻⁶⁴, and recent evidence suggests that optimal accuracy in reporting may be achieved with short follow-up periods (e.g., 30 days)⁵². Monthly online assessments will also measure general positive/negative affect over that time using the positive and negative affect scales of the PANAS-X⁶⁵, a 20-item scale that asks participants to rate various emotion words according to the extent they have “felt this way over the past month,” on a 1 (*very slightly*) to 5 (*extremely*) scale. These subscales have excellent psychometric properties when used to measure trait affect⁶⁵. Health empowerment will be measured each month using the Patient Activation Measure (PAM-13⁶⁶), and social support will be assessed with 3 subscales of the Received Support Scale (Emotional, Informational, Satisfaction). Both measures have excellent psychometric properties⁶⁶⁻⁶⁹.

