keep their phone near them as much as possible over the 7-month study. They will also be instructed to inform study staff as soon as possible should they lose their phones, change phones, or their current service contract lapses. One week after the initial appointment, an HBST kit will be sent to participants’ verified addresses. Shipment tracking will be used to record data about when HBST participants receive their tests. In “enhanced” HBST, participants, opening their mailed test enclosure will trigger an alert on the study database, which is monitored regularly by staff QHTCs. These alerts will instruct QHTCs to conduct a follow-up call with participants. QHTCs will be CAAS postdoctoral trainees with Ph.D.’s in clinical psychology who have completed additional training in HIV testing counseling (offered by [name]), suicide prevention intervention (offered by nearby Lifespan Hospital), and study-specific follow-up procedures. QHTCs will take turns placing follow-up calls. QHTCs will conduct calls while in private offices on Brown University’s campus. As such, they will be able to access the study database while conducting the calls, so as to allow check-ins about previous referrals and data entry during calls. QHTCs will follow up with participants within 24 hours after the test is opened. During follow-up calls, QHTCs will verify whether the participant has completed the test, what the result was, and ask whether the participant would like to receive counseling, entering this data into the study database. For reactive results, QHTCs will facilitate appointments for confirmatory testing. For non-reactive results, QHTCs will inquire about participants’ interest in other prevention services (e.g., STI testing, counseling). QHTCs will also screen for suicidality and record this information using the data entry forms, providing intervention/referral if needed. If participants indicate they have not taken the test yet but plan to do so, QHTCs will ask when they plan to take the test and whether there is a better time to contact them again. If a participant cannot be reached during the 24-hour post-test window, the 3 additional follow-up attempts will be made over the following 72 hours. This process will repeat for tests sent at 3 and 6 months. To facilitate monthly study assessments, participants will receive an email with a link to an each assessment specific to that participant and time period. Participants will be asked to complete these on a desktop computer within 2 days of receipt, and failing to do so within that time will prompt the RA to follow up via phone and email to encourage adherence. Once the study is complete, the RA will follow-up with participants over the phone to conduct a 30-minute qualitative interview. This interview will assess participants’

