Participants will be recruited from the community using ads in popular gay social networking mobile apps (e.g., Grindr, Jackd, Scruff). Participants expressing interest in the study will be screened online. Those meeting eligibility criteria will be contacted by phone and email to schedule an in-person appointment to begin the study. Next, participants will complete baseline measures online. Then, participants will be randomized to a condition. For those in the "enhanced" condition, RAs will inform participants about the study's purpose and guide them in downloading study software onto their smartphones. Although participants will not need to actively provide any input through the app, RAs will instruct participants to keep the app installed, their Bluetooth sensor enabled, and their phones near them throughout the 7-month study. RAs will also ask participants to notify them as soon as possible if they lose their phone or get a new one, their data is erased, or if their service plan changes. Next, RAs will inform all participants that they should expect to receive an email each month with a unique link, and that clicking this link will allow them to complete their monthly assessments. They will also be informed that HBST kits will be mailed to them 1 week after their appointment, and then again in 3 months and 6 months, which they can choose to take or not. However, should they choose to do so, those in the "enhanced" condition will be told that they should expect a call from a QHTC associated with the study within 24 hours after opening their test, and that these calls are intended to provide counseling and referrals after taking the test (which participants can refuse). Finally, participants will be asked to complete a 30-minute follow-up interview about the study via phone after completing the study. They will be informed that they can pick up payments for completing study assessments at the research offices anytime during or after the study.

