1. Focus groups will be conducted in-person during the study's start-up phase to solicit feedback about the mobile monitoring system. It will also solicit feedback about use and follow-up issues that will be used to refine the technology use (during the start up phase) and follow-up procedures (during the study phase).
2. Individual interviews will be collected over the phone during the start-up phase to collect feedback from individual high-risk MSM about their experiences using the mobile monitoring system that inform further refinement of the system and procedures used during the study phase. Phone interviews will also be conducted at the conclusion of the study among all participants to address general usability of HBSTs, preferences for follow-up, and experiences using the “enhanced HBST” system (for those in this condition). Phone interview data will also be collected during follow-up calls placed during the study phase to those in the “enhanced HBST” condition, and will assess whether participants used their test, what the result was, whether they would like to receive post-test counseling, whether they would like to receive referrals, and whether they followed up on any referrals offered during the previous follow-up calls.
3. Online questionnaires, will be used to collect screening, baseline, and monthly assessment data.
4. Online web application, used to specifically collect TLFB data in monthly assessments

Focus group data will be collected during in-person focus group meetings with members of the target population. These methods will produce qualitative data in the form of handwritten notes, digital recordings (collected using a digital voice recorder) and transcripts for analysis. Focus groups will be moderated by [name], and will generate data in the form of written notes, voice recordings, and transcripts, none of which will contain participant identifiers. Contact data will be collected via online screening to facilitate scheduling focus groups, but will be deleted after focus groups are completed. We will use this data to inform both the refinement of the “enhanced HBST” system and how we conduct follow-ups after testing during the study phase.

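### The secondary-outcome instruments are named only in the monthly surveys, so the plan names no pre-randomisation value on them and uses none in the analysis

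*Protocol*

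**What the plan says.** The Secondary Aims in Protocol C.1 are to "explore potential within- and between-subject effects of Enhanced HBST versus standard HBST" on affect, social support, sexual risk behaviour and health empowerment.

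Protocol C.4, Measures, describes the baseline content in one sentence: "Demographics, past HIV testing history, sexual behavior, and other relevant variables will be collected at baseline". The outcome instruments come after it, and each is attached to the monthly surveys:

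- **PANAS-X:** "Monthly online assessments will also measure general positive/negative affect over that time".
- **PAM-13:** "Health empowerment will be measured each month using the Patient Activation Measure". The three Received Support subscales are in the same sentence.
- **TLFB:** described with past-month recall among the monthly assessments. Section C.5.1 lists it as an "Online web application, used to specifically collect TLFB data in monthly assessments". The item directly above gives the online questionnaires a role at screening, baseline and monthly.

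On sequence, Protocol C.5 says: "Next, participants will complete baseline measures online. Then, participants will be randomized to a condition". Orientation to the enhanced arm follows. The Procedure text in C.4 adds: "One week after the initial appointment, an HBST kit will be sent".

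Under Planned Analyses/Power Considerations, the secondary outcomes are compared as means by condition and by testing status. No change from baseline and no baseline covariate is stated. The SAP's list of key outcomes contains none of these scales.

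**The concern.** A within-subject effect is easiest to interpret when each man has a score, on the same instrument, from before he was exposed to anything that differs between arms. The plan names no such score. A man who opens kit 1 in the first month would have no scheduled PANAS-X, PAM-13, Received Support or TLFB value from before opening it. A man who has not opened it by the first survey still answers knowing his arm.

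Three things are at stake:

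- **Precision.** The protocol wants to read the direction of effects from 20 men per arm. Stable between-person differences in affect, empowerment or support remain as noise when no baseline value is used.
- **A reference point for change.** Change measured from month 1 starts after randomisation and, for some men, after the first test and call.
- **The comparison by testing status.** Using a kit is a choice made after randomisation, so randomisation does not protect this contrast. If men who test already differ in affect or empowerment, a score from before the first kit is the direct way to see it.

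**Working it through.** The plan gives no power figure to reproduce, so the check is of the schedule first and of size second.

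**1. Do the monthly surveys include the baseline?** The protocol pays $20 for the baseline visit and, separately, $15 per monthly assessment to a total of $105. $105 / $15 = 7 surveys over a 7-month study. No monthly survey doubles as the baseline visit.

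**2. When is the first monthly survey relative to kit 1?** Kit 1 is sent at day 7. No day is stated for the first survey. Assume day 30, and use the ±5-day on-time window as the range:

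| First survey completed | Days after kit 1 was mailed |
|---|---|
| Day 25 | 25 − 7 = 18 |
| Day 30 | 30 − 7 = 23 |
| Day 35 | 35 − 7 = 28 |

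At day 30, a 30-day recall reaches back only to the baseline visit. 7/30 = 23% of it precedes the mailing of kit 1, and all of it follows randomisation.

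**3. What is named before randomisation, by domain?**

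| Domain | Named at baseline | Instrument named for the monthly surveys |
|---|---|---|
| Sexual risk | Yes, instrument and recall period not given | TLFB |
| Affect | Not named | PANAS-X |
| Empowerment | Not named | PAM-13 |
| Social support | Not named | Received Support (3 subscales) |

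The last three may fall under the open-ended end of the baseline sentence. The text does not say.

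**4. Size of the precision loss.** Work in units of the between-person SD of the outcome, with n = 20 per arm.

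- SE of the unadjusted difference = √(2/20) = 0.316 SD.
- A chance baseline difference has the same SD. P(|Z| > 1) = 0.32, so a difference of at least 0.32 SD arises in about 32% of randomisations. For 0.5 SD, 0.5/0.316 = 1.58 and P(|Z| > 1.58) = 0.11.
- Adjusting for a baseline value with correlation r multiplies the variance by (1 − r²). The documents give no r.

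| Assumed r | Variance cut r² | SE = 0.316 × √(1 − r²) | Detectable difference |
|---|---|---|---|
| none used | 0% | 0.32 SD | 0.89 SD |
| 0.5 | 25% | 0.27 SD | 0.77 SD |
| 0.7 | 49% | 0.23 SD | 0.63 SD |

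The last column is illustrative: two-sided 5%, 80% power, normal approximation, (1.96 + 0.84) × SE. The protocol sets no such target. Estimating the slope with 40 men gives a little back: a factor of about 1 + 1/(40 − 4) = 1.03 on the variance, so the cuts become 1 − 0.75 × 1.03 = 23% and 1 − 0.51 × 1.03 = 47%.

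**5. Effect on reading direction.** Take an assumed true effect of 0.3 SD. The chance that the estimate has the wrong sign is Φ(−0.3/SE): Φ(−0.95) = 17% unadjusted, Φ(−1.10) = 14% at r = 0.5, and Φ(−1.33) = 9% at r = 0.7.

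**The case against.** A reader might infer that the secondary outcomes have no pre-intervention value at all, that within-subject effects therefore cannot be estimated, and that the arm comparison is compromised. The documents do not support this.

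- **Sexual behaviour is collected at baseline**, and C.5 puts baseline before randomisation. What is missing is a statement that the TLFB is the instrument.
- **For affect, empowerment and support the plan is silent.** The baseline sentence is open-ended, and the online questionnaire channel serves baseline as well as the monthly surveys. Figure 3, the assessment timeline, might settle the point but could not be read.
- **The between-arm comparison is valid by randomisation** without any baseline. Chance imbalance at 20 per arm is ordinary sampling error and already sits in the 0.32 SD standard error.
- **Repeated surveys allow some within-person comparison.** Kits are optional and sent three times, and the call is triggered by opening the enclosure, not by mailing it. Seven monthly values permit contrasts around kits 2 and 3 and between tested and untested months.
- **The aims are exploratory.** The protocol calls its analysis mainly descriptive and acknowledges the limits of small studies. The gain in step 5 is real but modest.

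All of this stands, and it narrows the point. It does not remove it. A sexual-behaviour item of unknown form and recall cannot be set against a past-month TLFB count. Contrasts around later kits do not give a pre-exposure value to a man who opened kit 1 in month 1. Nothing in the Planned Analyses or the SAP uses a baseline value, even if one is collected.

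**Conclusion.** The point holds as a gap in specification and a missed gain in efficiency, with moderate confidence because the timeline figure could not be read. The plan names no pre-randomisation value on the four outcome instruments and uses none in the analysis, although within-subject effects are a stated secondary aim.

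The between-arm estimate is not biased by this. The costs are:

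- a standard error of 0.32 SD where 0.23 to 0.27 SD was available, a variance cut of about 25% to 49%, if r is 0.5 to 0.7 (assumed);
- no pre-exposure reference for men who open kit 1 in month 1; and
- no means of seeing prior differences in the comparison by testing status.

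The placement of the first survey after kit 1 is mailed rests on the natural reading of a monthly schedule (day 30 assumed). It is worth correcting because the remedy is cheap, but it does not threaten the main aims.

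**What to change.** 1. In C.4, Measures, and C.5.1, name PANAS-X positive and negative affect, PAM-13, the three Received Support subscales and a 30-day TLFB as part of the baseline session, completed before randomisation. If the unspecified baseline variables already include them, say so and list them.
2. In the Planned Analyses and the SAP, compare arms on each secondary outcome's follow-up mean adjusted for the participant's own baseline value, and report the estimate with its confidence interval.
3. Measure within-subject change from baseline, not from month 1.
4. For the comparison by testing status, show baseline values by group and adjust for them. State that the comparison remains observational, since baseline adjustment does not make it randomised.

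The cost is a somewhat longer baseline session; the documents give no completion times from which to size it. The visit is already scheduled and paid, baseline measures are already taken online, and the instruments are already needed for the monthly surveys. No visit is added.

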Those in the "enhanced" HBST condition will receive follow-up calls within 24 hours after opening their tests. These calls will be made by CAAS Postdocs who have Ph.D.'s in clinical psychology and who will receive training in HIV test counseling (provided by [name]) and suicide prevention intervention (provided by behavioral health staff at The Miriam Hospital). Training by [name] will involve modeling counseling interactions, role playing with QHTCs, and direct observation during clinic-based testing conducted at the Miriam Immunology Clinic. [name] will also provide ongoing supervision to these QHTCs throughout the study. Follow-up calls will follow the CDC's guidelines for HIV counseling, testing, and referral⁸⁰, and as such, will involve the same post-test counseling procedures offered by paraprofessionals and service providers in clinic- and community-based settings worldwide. Participants will be screened for suicidality during these calls, and if necessary, intervention will be provided according to National Suicide Prevention Lifeline procedures^{81,82}. Referrals will be offered to local, LGBT-friendly agencies for additional HIV/STI testing, additional HIV prevention services (PrEP, risk reduction counseling), substance abuse treatment, mental health treatment, and primary care. During 3- and 6-month follow-up calls, QHTCs will also assess whether referral for these specific services was provided during the previous call, and if so, whether the participant sought these services (questions also assessed via monthly online assessments). For participants testing positive, participants will be assured that an initially reactive result is not a confirmed positive result, and will be scheduled for an appointment to conduct confirmatory testing at The Miriam

Immunology Clinic (MIC) as soon as possible. The MIC has standard procedures for providing newly diagnosed patients ongoing HIV care.

All study procedures, including data collection, will be conducted by research staff, the PI ([name]) or Co-Investigators ([name] and [name]). Research staff will receive intensive training in all study procedures from [name], [name], and [name].

C.5.1 Sources of Materials

Self-report data collected from participants throughout the course of the study will be obtained using the following methods:

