Several measures will also be employed to minimize psychological discomfort or distress as a result of the research. First, while participants may experience some discomfort while taking an HIV test at home, past research suggests that this risk is low⁴²⁻⁴⁴, and OraSure's clinical trial data suggests that HBST can be completed safely, resulting in minimal distress. The FDA has also deemed that this product can be used safely by the general public. Nevertheless, participants in either condition will be encouraged to report any distress they experience as a result of testing to study staff, who will provide referral to LGBT-friendly treatment providers in the local area. Second, while some participants may receive "reactive" results during the study, staff will prepare them for this during their orientation visit and encourage participants to interpret this merely as "reactive" (rather than "positive"), since further testing is needed to confirm "positive" results. Participants in either condition will also be encouraged to report receiving "reactive" results to study staff as soon as possible, and will be provided with contact information for doing so. These participants will then be scheduled for confirmatory testing appointments at MIC, which has established procedures for conducting follow-up testing and engaging these patients in care. Finally, the risk of distress or discomfort from study assessments is low, but participants will again be encouraged to report this to study staff as soon as possible. Staff will then provide referrals to local MSM-friendly treatment resources and emergency services. In addition, research staff will be trained in responding to adverse events, including participant distress. These events will be reported promptly to the Brown University IRB.

Finally, to ensure that *all* participants are encouraged to seek follow-up testing and care after testing, participants indicating that they have taken a test on the monthly assessment (either

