provided by us or from another clinic) will be asked what the results of this test were. If it was reactive or positive, we will ask whether confirmatory testing has been completed or is pending and whether participants are currently under the care of a physician who is attending to these issues. For those noting having received a “reactive” result from a study test, who is not pursuing confirmatory testing and/or is not under the care of a physician who is aware of this issue, we will follow-up with these participants as soon as possible over the phone. The monthly assessment data will only contain participants’ unique study ID numbers, and will not be identifiable until it is downloaded and imported into the study databases. We will download and monitor the study monthly survey data every 48 hours, and for every participant with this constellation of responses, we will follow up with them over the phone to offer to make appointments with them for confirmatory testing and follow-up care.

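### The monthly survey asks about unlinked reactive or positive results from any test, but the written call rule clearly covers only study-kit results

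*Protocol*

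**What the plan says.** The relevant text is the last paragraph of Protocol D.2 (Procedures to Protect Against Risk). Its stated purpose is "to ensure that *all* participants are encouraged to seek follow-up testing and care after testing". It then proceeds in four steps.

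- **Result question.** It goes to anyone reporting a test, from either source: "provided by us or from another clinic) will be asked what the results of this test were".
- **Linkage questions.** "If it was reactive or positive, we will ask whether confirmatory testing has been completed or is pending", and also whether a physician is attending to the matter.
- **Call rule.** Staff telephone those noting a reactive result "from a study test, who is not pursuing confirmatory testing and/or is not under the care of a physician" who knows of it.
- **Staff review.** Survey data are checked every 48 hours, and "for every participant with this constellation of responses, we will follow up with them over the phone" to offer appointments.

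Other parts of the Protocol bear on the same man:

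- D.2 encourages participants in both arms to report reactive "results to study staff as soon as possible, and will be provided with contact information for doing so". Staff then schedule confirmatory testing. This is not expressly limited to study kits.
- C.1 (Overview of the research) and C.4 (Experimental conditions) have standard-arm kits mailed with contact details for local services. C.1 lists HIV care and confirmatory testing among them.
- C.4 (Procedure) and C.5 provide counselor calls in the enhanced arm only, prompted by the opening of a study kit. At 3 and 6 months, "QHTCs will also assess whether referral for these specific services was provided during the previous call" and whether those services were sought.
- C.4 (Measures) describes the survey more narrowly: "participants will complete online assessments each month inquiring about whether they used a study-provided HBST kits in the last month", and with what result. It is D.2 that extends the result question to tests done elsewhere.

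**The concern.** The survey gathers more than the call rule acts on. A man who tests at another clinic, has a reactive or positive result, and answers that he is not pursuing confirmation or has no physician attending to it has told the study exactly what the paragraph was written to detect. Staff would hold that report within the 48-hour review cycle, yet the written rule would not clearly direct them to call.

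Outside testing is something the trial itself encourages. Enhanced-arm calls offer referral for additional HIV testing (C.5), standard-arm kits carry local service contacts (C.4), and the survey asks whether additional HIV testing was sought (C.4, Measures). The Protocol's background also singles out men who know of their infection but are not engaged in care as a major source of transmission. What is at stake is a delay in care for an individual participant, not the validity of an estimate.

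**Working it through.** **Scope comparison.** The plan states no figure to reproduce, so the main check is to set the steps of the D.2 paragraph side by side.

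| Step | Test source | Result | Linkage status |
|---|---|---|---|
| Result question | study kit or other clinic | any | not yet asked |
| Linkage questions | study kit or other clinic | reactive or positive | asked |
| Call rule | study test | reactive | no confirmatory testing and/or no physician care |
| 48-hour review | by reference back | by reference back | by reference back |

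The first two rows cover both test sources and the third covers one. The phrase in the review sentence, "for every participant with this constellation of responses, we will follow up with them over the phone", names no test source. Its nearest antecedent is the study-test sentence, so the natural reading carries the same limit. A looser reading, in which it means any reactive or positive and unlinked survey pattern, is possible. No other section supplies a survey-triggered call for a clinic result.

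**Other routes for the same man.**

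- Contacting staff himself: available in both arms, but depends on his initiative.
- Service contacts mailed with the kit: standard arm, also dependent on his initiative.
- Counselor call: enhanced arm only, and only if he opens a later study kit. None is sent after the third.
- A later study kit in the standard arm: leads to a call only if it is used, reactive and reported as unlinked.

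None of these is prompted by the clinic result he has reported on the survey.

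**Frequency.** The sample size of 40 is from C.1. The documents give none of the rates, so these are assumptions: 10% to 50% of men test at another clinic during the study, 1% to 5% of those have a reactive or positive result, and 10% to 30% of those report being unlinked. With p the product of the three rates, the expected number is 40p and the chance of at least one is 1 − (1 − p)^40.

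| Case | p | Expected men | Chance of at least one |
|---|---|---|---|
| Low | 0.10 × 0.01 × 0.10 = 0.0001 | 0.004 | 0.4% |
| Mid | 0.25 × 0.03 × 0.20 = 0.0015 | 0.06 | 5.8% |
| High | 0.50 × 0.05 × 0.30 = 0.0075 | 0.30 | 26.0% |

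If every man with an outside reactive or positive result at the high end were unlinked, the number to call would be 40 × 0.50 × 0.05 = 1.0.

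**The case against.** The best case for the plan is that limiting the rule to study kits is a reasonable choice of scope. A reactive result at home with no provider present is the hazard the study creates; a clinic result is not, and the clinic has already given the man a provider contact. This stands as an explanation for most clinic-tested men. It does not answer the case of the man who himself reports no confirmation or no physician care. The protocol chose to put that question to clinic-tested men, under an aim that covers all participants.

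The ambiguity of the review sentence also stands in part: a staff member could reasonably read it as covering clinic results. That is a reason to settle the wording.

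The objection on frequency is largely right. In the mid case there is about a 94% chance that nobody is affected. The high case needs all three assumed rates at their upper ends, and having half the cohort test elsewhere is hard to credit when entry requires no HIV test in the past year (C.2).

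A reader might infer that such a man is left without a route to care, or that staff may not call him. The documents support neither. He can report to staff at any time and be scheduled for confirmatory testing, and nothing bars staff from acting on what they read. A reader might also measure the delay by the wait for the next kit. That is not the relevant alternative, because he can contact staff directly and no kit follows the third. Nor is the absence of the word 'positive' from the call rule a second gap: the protocol trains participants to call kit results reactive, so its absence follows from the study-test limit.

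**Conclusion.** The point holds as a mismatch of scope within one paragraph. On its most natural reading the call rule is narrower than both the questions that feed it and the aim that introduces it, so an unlinked reactive or positive clinic result reported on the survey is not clearly covered by a staff call.

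The expected number affected is probably well under one man in 40. That rests wholly on assumed rates, and the range is wide. No planned analysis is materially affected. The change is worth making because the consequence for an individual could be serious and the correction is very cheap. It is a low-frequency safety improvement and not evidence that the trial's protections fail in general.

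**What to change.** In the last paragraph of D.2, change the trigger to *a reactive or positive result from any test reported on the monthly assessment*. Keep the existing conditions on confirmatory testing and physician care, and apply the same rule in the 48-hour review. Record each such call with its date and study arm.

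The change is one sentence and uses the existing survey questions, staff and review cycle. At the upper limit of the assumptions it adds about one man to call. Some of these men may already be under an outside clinic's management, and the call can open by asking about that.

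There is also a small cost to the comparison. Calls in the standard arm add a little active linkage to the condition meant to be passive, which touches Aim 2c. The existing rule already allows the same kind of call for study-kit results in both arms, and at these numbers the addition is negligible. The call record lets it be noted when linkage is compared.
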